After trimming, strata of propensity scores will be used to frequency match users of corticosteroids with users of tacrolimus and pimecrolimus. A matching ratio up to 4:1 (corticosteroids to tacrolimus or pimecrolimus), depending on available matches, will be used across strata.

In the JOELLE Extension, the patient characteristics will be described for the study cohorts before and after matching. This will allow the investigators to evaluate the efficiency of the frequency matching conducted. In addition, the baseline characteristics of patients excluded after trimming will be also described to identify subgroups (e.g. more severe patients) for whom the results of the study cannot be generalized.

The strata of propensity scores will be used to stratify person-time of follow-up and number of events for each defined exposure category. This will allow investigators to conduct a stratified analysis with aggregated data from each data source. Mantel-Haenszel methods for stratified data will be used to estimate pooled measures of effect. Additional stratification by type of prescriber of first prescription as a proxy for severity of atopic dermatitis was conducted in PHARMO and Sweden in Phase I and will be conducted in PHARMO, Sweden, and Denmark in the JOELLE Extension, the study data sources where this variable is available. Initially, the propensity scores and counts will be summarized into deciles by combining data from contiguous strata; if this results in cell counts that are too small, some deciles may be further combined, resulting in fewer strata.

Each database research partner will apply the study definitions to calculate person-time of exposure and number of events associated with each exposure category and endpoint definition. Using these data in conjunction with propensity scores, each database research partner will create an exposure summary table containing the essential data for measuring the effect of exposure on the study outcomes while adhering to the restrictions that are imposed on the release of individual-level data from each site.

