9.7.2.1 Stratification by Type of Prescriber (Dermatologist vs. Other Prescribers)

Data from prior studies and from Phase I of the JOELLE study have shown that type of prescriber of the first prescription (e.g., dermatologist versus nondermatologist) can be a confounder of the association between study medications and skin cancer [23]. In Phase I, information on type of prescriber was available in PHARMO and Sweden but not in Denmark or the CPRD. We evaluated the confounding effect of type of prescriber through a quantitative bias analysis for unmeasured confounders to account for the lack of information in Denmark and CPRD. In the JOELLE Extension, information on type of prescriber is also available in Denmark. To evaluate the potential bias for the uncontrolled effect of type of prescriber in the CPRD, an additional analysis restricted to users in PHARMO, Denmark, and Sweden will be conducted in the JOELLE Extension. Based on the number of users included in Phase I, this additional analysis is estimated to include approximately 90% of children and 79% of adults from the whole study cohort (including the CPRD).

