9.7.2.5 Sensitivity Analysis

Sensitivity analyses will be conducted for single use of topical tacrolimus and topical pimecrolimus. The following sensitivity analyses will be conducted:

1. Incidence rates and incidence rate ratios will be estimated for the subgroup of children aged ≥ 2 to < 16 years, which is the age range for children specified in the labeling of topical tacrolimus.
2. Incidence rates and incidence rate ratios will be estimated for the occurrence of each specific endpoint regardless of a prior occurrence of any of the other study endpoints during the study period.
3. Incidence rates and incidence rate ratios will be estimated for the occurrence of all MMs and NMSCs excluding in situ carcinomas, to evaluate the role, if any, of the inclusion of noninvasive skin carcinomas.
4. Incidence rates and incidence rate ratios will be estimated for basal cell carcinoma and squamous cell carcinoma separately.
5. Incidence rates and incidence rate ratios will be estimated for cutaneous and noncutaneous lymphomas separately.
6. Incidence rates and incidence rate ratios will be estimated by strata of propensity scores to explore effect modification.
7. To evaluate protopathic bias, incidence rates and incidence rate ratios will be estimated for the first 6 months after the first exposure (ignoring lag time), and for other lag times (e.g., 12 months, 18 months, 24 months, 48 months) in addition to the predefined lag time of 6 months.
8. To explore potential surveillance bias, incidence rates of malignant melanoma and non-melanoma skin cancer will be stratified by stage of malignancy at the time of diagnosis in those data sources where information on stage is available. Data on stage of cancer at diagnosis can be useful to assess the potential role of a higher medical surveillance in the detection of cases (if lower stages are found, higher medical surveillance is likely to have occurred).
9. Incidence rates and incidence rate ratios will be estimated by severity of atopic dermatitis. In Phase I, definition of severity of atopic dermatitis was based on the utilization of health care resources. However, information was only partially available in the study data sources. In the JOELLE Extension, severity of atopic dermatitis will be defined according to the type of prescriber of the first prescription (dermatologist or nondermatologist) as a proxy for severity.

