We assumed that topical tacrolimus and topical pimecrolimus are prescribed only for atopic dermatitis and that members of these cohorts are not required to have a recorded diagnosis of atopic dermatitis. However, some patients may be prescribed these medications for skin disease other than atopic dermatitis. Bias from misclassification of atopic dermatitis among these patients could be present if the risk of skin malignancies associated with the underlying skin disease for which these medications are prescribed differs from the risk associated with atopic dermatitis. The magnitude of the bias would depend on the proportion of patients prescribed topical tacrolimus or topical pimecrolimus to treat skin disease other than atopic dermatitis. However, skin diseases that could be treated with these medications are infrequent, particularly in children, and may include inverse psoriasis (flexural psoriasis) and facial psoriasis [24]. For other skin diseases, such as vitiligo and alopecia areata, there seems to be limited effect of topical tacrolimus or pimecrolimus, and both diseases are slightly more common among children with atopic dermatitis [25,26]. Other disorders such as pyoderma gangrenosum, cutaneous lupus erythematosus, and oral lichen are even rarer in children [27-29]. Lichen sclerosus et atrophicus (LSA) is also uncommon in children [30]. LSA usually responds very well to treatment with very potent topical corticosteroids (clobetasol propionate), which reduces the need for topical tacrolimus or pimecrolimus [30]. Overall, these data indicate that the magnitude of a potential bias caused by misclassification of atopic dermatitis in users of topical tacrolimus and topical pimecrolimus will probably be low. To minimize potential bias, we will include in the estimation of propensity scores individual variables for specific skin diseases that potentially can be treated with topical tacrolimus or topical pimecrolimus. Several databases capture only partial information about the occurrence or severity of atopic dermatitis. During the JOELLE Extension, we plan to use type of prescribing physician (dermatologist or nondermatologist) as a proxy for severity of atopic dermatitis.

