Annex 3.

Summary of Characteristics of Databases

Table A3-1. Protopic and Malignancies: Main Features of Databases and Data Availability

Characteristic	CPRD, UK	PHARMO Netherlands	Danish Health Databases	Swedish National Registers
Database population in 2015 (million)	4.4	4.0	5.7	9.7
Database type	Primary health care electronic medical record database plus linkage to hospital data (Hospital Episodes Statistics [HES]) and cancer registry data	PHARMO Database Network holds several databases, linked on patient level. For this study, outpatient pharmacy data (dispensed drugs), hospitalization data, GP data, pathology data (PALGA), and Netherlands Cancer Registry (JOELLE Extension) data will be used.	Prescription registry (all reimbursed drugs dispensed by prescription since 1995) Danish National Registry of Patients (hospital admissions, outpatient visits, and emergency department visits) Cancer registry	Prescribed Drug Register (all drugs dispensed by prescription since July 1, 2005) Patient registers (hospital admissions and outpatient visits) and primary care database Cancer Register Register of the Total Population
Tacrolimus reimbursement approval	April 2002	November 2002	June 2002 Change in December 2008 (can be prescribed by MDs other than dermatologists)	June 2002
Study data: phase 1 availability timelines	2011 Data: CPRD: 1Q 2012 (data updated every 3-4 months; lag time 6-12 weeks) CPRD-HES: 3Q 2012 CPRD-cancer data: 2014	2011 Data: 3Q 2012 Hospital data: yearly available (7 months lag time) Complete database update: annually Q3, includes hospitalization data available up to previous year December (7 months lag time) Pharmacy, GP, PALGA available up to Q3	2011 Data: Mid 2012 Prescription data: annually available at midyear (lag time 6-18 months)	2011 data: Rx data: 3Q 2012 Cancer data: 1Q 2013 Prescription data (since July 1, 2005): 1 month lag time Cancer Register: 1 year lag time Patient Register: Up to 8 months lag time

Characteristic	CPRD, UK	PHARMO Netherlands	Danish Health Databases	Swedish National Registers

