Linkages	Half of CPRD practices (England) linked to HES database through NHS ID. Linkage update every 3 months (4-7 months delay) CPRD linkage to Cancer Regional Registries (partial) through NHS ID (2 years delay)	All databases in PHARMO Database Network are probabilistically linked: pharmacy and hospitalization are core databases, Netherlands Cancer Registry, PALGA database and GP database need permission for use. GP data: ~8%	Linkage through Civil Personal Registration (CPR) number	Linkage of databases through CPR
Restrictions/ Regulations			Individual prescription data cannot be transferred to researchers	
Demographics				
Unique identifier	Yes (patient NHS ID)	Yes	Yes (CPR)	Yes (CPR)
Registration date	Yes (GP practice registration)	Yes		
Date of birth	Yes	Yes	Yes	Yes
Gender	Yes	Yes	Yes	Yes
Date of death	Yes	Yes	Yes	Yes
Drugs				
Unique product code	Yes	Yes	Yes	Yes
Drug coding classification	Multilex/British National Formulary	ATC	ATC	ATC
Online drug formularies	By registration only http://bnf.org/bnf/index.htm	https://www.farmacotherapeutischkompas.nl/	http://dkma.medstat.dk	http://formulary.drugplan.health.gov.sk.ca/

Characteristic	CPRD, UK	PHARMO Netherlands	Danish Health Databases	Swedish National Registers
Prescribed/ dispensed drugs	GP prescriptions	Dispensed (independent of reimbursement)	Danish prescription registry (reimbursed drugs dispensed by prescription)	Swedish prescription drug register (all drugs dispensed by prescription since 2005 independent of reimbursement)
Date drug prescribed/ dispensed	Yes	Yes, date dispensed	Yes	Yes
Drug indication	Associated with new courses of medications, but completeness is variable	No	No	No
Dose	Yes (Prescribed dose)	Yes	Yes (cumulative dose)	Yes
Formulation	Yes	Yes	Yes	Yes
Treatment duration	As indicated by the prescription	Yes, as indicated on the dispensing	No	No
Type of prescriber	GP	Yes	Yes, in JOELLE Extension	Yes
Inpatient drugs (cytostatics)	Pending	Indirectly (based on hospitalization for chemotherapy); no specific drug names For a small subset, inpatient data available including information on type (ATC code)	Drug-specific codes available	Mostly administered at hospitals. Drug-specific codes available (underreported but improving)

Characteristic	CPRD, UK	PHARMO Netherlands	Danish Health Databases	Swedish National Registers
Study variables and data validation				

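### In Denmark the prescriber-based severity proxy for tacrolimus is tied to a rule change in December 2008, so the Danish severity strata partly reflect that rule and calendar period

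*Protocol*

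**What the plan says.** Protocol section 9.7.2.5, item 9, plans rate ratios by severity of atopic dermatitis. The Phase I definition, based on health care use, is replaced because the data were only partly available. In the Extension, "severity of atopic dermatitis will be defined according to the type of prescriber of the first prescription (dermatologist or nondermatologist"). No country or calendar limit is attached. Section 9.9 repeats the plan without a caveat: "we plan to use type of prescribing physician (dermatologist or nondermatologist) as a proxy for severity of atopic dermatitis".

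Denmark is new to this. Section 9.7.2.1 states: "In the JOELLE Extension, information on type of prescriber is also available in Denmark". Section 9.7.1.4 says that stratification by prescriber, described there as a severity proxy, "will be conducted in PHARMO, Sweden, and Denmark in the JOELLE Extension".

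Annex 3, Table A3-1, in the row on tacrolimus reimbursement approval, gives for Denmark: "June 2002 Change in December 2008 (can be prescribed by MDs other than dermatologists"). The same table describes the Danish drug data as "Danish prescription registry (reimbursed drugs dispensed by prescription"). Section 9.2.1 sets inclusion from first availability through the end of 2014, which spans the change.

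**The concern.** A severity proxy has to vary with severity in both arms. If tacrolimus in Denmark was tied to dermatologists until December 2008, prescriber type carries little information on severity among earlier Danish tacrolimus starters, because mild and severe cases would mostly share the label. Annex 3 documents no such rule for topical corticosteroids, so comparators from the same years can fall in either stratum.

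Two distortions follow. In the Danish dermatologist stratum, tacrolimus users of mixed severity are set against corticosteroid users who reached a dermatologist by other routes. In the Danish nondermatologist stratum, tacrolimus users come mainly from late calendar years, while comparators may come from any year. A difference between strata, or the lack of one, could then be credited to severity when it reflects the rule and the period. This matters because section 7.1 cites relative risks of lymphoma of 2.4 and 3.7 in severe atopic dermatitis, and item 9 is where the tacrolimus comparison is examined by severity.

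**Working it through.** The protocol gives no figure to reproduce on this point. The check sets the sections side by side and then sizes the affected period.

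**1. Is the rule reconciled anywhere?** Sections 9.7.1.4, 9.7.2.1, 9.7.2.5 and 9.9 all use prescriber type. None mentions the December 2008 change, limits the Danish severity analysis to later starters, or splits it by period.

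**2. Danish inclusion window before the change** (dates from Annex 3 and section 9.2.1)
- June 2002 to November 2008: 7 + 5 × 12 + 11 = 78 months.
- June 2002 to December 2014: 7 + 12 × 12 = 151 months.
- Share: 78 / 151 = 52%.

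**3. Available follow-up by stratum, to the end of 2015**
- A tacrolimus user starting in December 2008 has at most 1 + 7 × 12 = 85 months, about 7.1 years.
- A corticosteroid user starting in June 2002 can have up to 7 + 13 × 12 = 163 months, about 13.6 years.
- In the Danish nondermatologist stratum the two arms can therefore differ markedly in start year and length of follow-up.

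**4. Share of tacrolimus users who started before about 2009.** No Danish counts by year are given. As a rough guide for all databases, users with 7 or more years of follow-up at the end of 2015 started before about 2009 (Tables 5 and 6, cumulative columns):

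| | 6+ years | 7+ years | 8+ years |
|---|---|---|---|
| Children, of 25,479 | 11,132 (44%) | 8,348 (33%) | 6,250 (25%) |
| Adults, of 103,175 | 48,470 (47%) | 37,523 (36%) | 27,794 (27%) |

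The 6- and 8-year columns show how far the result depends on the cut. Early starters who died or left the database have shorter follow-up and are missed by this count.

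**5. Share of person-years in the 7+ year group.** Each row of Tables 5 and 6 is multiplied by its interval midpoint (0.5, 1.5, …, 13.5) and summed.
- Children: 76,370 / 146,020.5 = 52%.
- Adults: 338,507.5 / 602,953.5 = 56%.

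**6. Does the propensity score repair it?** Annex 5 lists calendar year of start date as a covariate. Scores are estimated and matched within each database on the whole child or adult cohort (sections 9.2.3.2 and 9.7.1.4), and balance there does not guarantee balance inside a prescriber stratum. Calendar year is not among the stratification factors in section 9.7.2.3. Even perfect calendar balance would not make prescriber type indicate severity in years when a rule largely determined it.

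**The case against.** The Annex 3 entry stands in a reimbursement row. A reader might infer that other doctors were barred from prescribing before December 2008, so that every earlier Danish tacrolimus user is in the dermatologist stratum. The document does not say that. Coverage limited to reimbursed drugs would give much the same result in the data if reimbursement is settled per dispensing, but the wording does not settle whether it is per dispensing or per product. This objection stands: the claim is probable and partial, not absolute.

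A reader might also take item 9 for the only severity analysis left. It is not. Section 9.7.2.6 stratifies corticosteroids versus untreated by prescriber for the same purpose, and Annex 5 keeps severity and dermatologist visits among the propensity score variables. Nor do the documents support tying the calendar effect to a change in Danish skin cancer reporting: the only dated change in Annex 3, for basal cell carcinoma, is Swedish.

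It might seem to follow that section 9.7.2.1 should be restricted too. That section treats prescriber as a confounder of the skin cancer association and asks what its absence in the CPRD does. That purpose does not depend on prescriber measuring severity.

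Two further replies stand in part. Section 9.7.2 already plans estimates within each data source, so Denmark could be read apart, although it does not mention item 9. The analysis plan is to be adapted to each database and could carry a Danish date split. The protocol itself, however, fixes the proxy without limit and adds Denmark.

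**Conclusion.** The point holds for item 9 of section 9.7.2.5, tacrolimus versus corticosteroids, Denmark. As written, the Danish severity strata are partly a prescribing or reimbursement rule and a calendar period, and the pooled severity result inherits this.

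The size rests on three assumptions. The first is that the December 2008 entry means a link to dermatologists before that date, which is the natural reading of a recorded change. The second is that this link shows in the Danish dispensing data. The third is that Denmark resembles the four databases together, with 33% of children and 36% of adults starting before about 2009 (25% to 44% and 27% to 47% over the cuts shown) and a little over half of person-years. The third is the weakest: a restriction may itself have held down early Danish uptake, while Swedish prescription data begin only in July 2005, which lowers the early share in the pooled figures.

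The documents do not show an effect on the main analysis, the pimecrolimus comparison, or corticosteroids versus untreated.

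**What to change.** For item 9, tacrolimus versus corticosteroids, in Denmark only:

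1. Split the start dates of both cohorts at December 2008.
2. Base the Danish severity interpretation on the later starts.
3. Report the pooled severity result with and without the earlier Danish starts, and for PHARMO plus Sweden alone.
4. State the rule as a limitation in section 9.9, and say there whether it governed prescribing or only reimbursement.

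Leave section 9.7.2.1, the pimecrolimus analysis and section 9.7.2.6 as they are.

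The cost is one extra date split at the Danish site, and Danish estimates for the later period that are less precise and have shorter follow-up. Splitting is preferable to discarding the earlier Danish starters. If Denmark resembles the pooled figures, discarding them would remove about a third of its tacrolimus users but more than half of the person-years, and the longest follow-up in a cancer study. With the split, no data are lost.

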9.7.2.6 Secondary Analysis

The secondary analysis will address the secondary study objective of estimating incidence rates and incidence rate ratios of skin cancer and lymphoma in users of topical

corticosteroids compared with untreated patients. The analyses will be conducted using the corticosteroids cohort identified in the comparison with users of tacrolimus. Each database research partner will individually match untreated patients with the corticosteroids cohort by year of birth, sex, calendar year of start date, and primary care general practice/region, at a matching ratio up to 4:1. Each database research partner will stratify the data simultaneously by year of birth, sex, calendar year of start date, and primary care general practice/region and will compute person-time and endpoint counts for each stratum. The coordinating center will estimate crude and standardized incidence rates and will use Mantel-Haenszel methods to estimate crude and adjusted incidence rate ratios for each database and overall across databases. To assess potential reverse causation among users of topical corticosteroids, incidence rate ratios will be estimated by time since first exposure to topical corticosteroids. Also, to evaluate the effect of severity of atopic dermatitis, the analysis will be stratified by type of prescriber of the first prescription (dermatologist or nondermatologist) of topical corticosteroids.

9.8 Quality Control

The standard operating procedures of each database research partner will be used to guide the conduct of the study. These procedures include internal quality audits, rules for secure and confidential data storage, methods to maintain and archive project documents, quality-control procedures for programming, standards for writing analysis plans, and requirements for senior scientific review.

All programming written by one study analyst will be independently reviewed by a different analyst, with oversight by a senior statistician. All key study documents, such as the statistical epidemiological analysis plan, abstraction forms, and study reports will undergo quality-control review, senior scientific review, and editorial review.

At the coordinating center, an independent Office of Quality Assurance performs audits and assessments that involve various aspects of its projects, including but not limited to documentation of education and training, data entry, data transfer, and RTI International institutional review board approval. Such audits in RTI will be conducted by the Office of Quality Assurance according to established criteria in standard operating procedures and other applicable procedures. Each of the database research centers will follow its own quality and audit trail procedures. The quality and audit trails at each center may be different.

A quality-assurance audit of this study may be conducted by the sponsor or the sponsor's designees.

Appropriate data storage and archiving procedures will be followed (i.e., storage on CD-ROM and DVD), with periodic backup of files to tape. Standard procedures will be in place to restore files in the event of a hardware or software failure at each research center.

